5.3.3 Group C – Eligibility criteria

The inclusion criteria for the NWG facilitator group are;

- An employee of either ICMHS or LikeMind, or delivering services in collaboration with either service (e.g. in-kind services, or private practitioner),
- Participated in a NWG facilitator training workshop,
- Facilitated at least one NWG,
- Willing to complete an anonymous survey on the organisations readiness to implement NWG and participate in a focus group on their experiences delivering the program.

5.4 Recruitment (Groups A and B)

The research team will attend a facilitator training to introduce the project and explain the research steps and processes. Recruitment flyers will be distributed at each of the study sites (See Appendix 12.1). Each location will have a study co-ordinator (TC, LikeMind, and PD, ICMHS) who hold managerial positions in each study site. The study site co-ordinator at each site will provide treating clinicians with an overview of the study and NWGs. Clinicians can then discuss participation with existing clients on their caseload and provide them with information on the study and the contact details of the research team. Some treating clinicians will also be trained NWG facilitators, however, they will not enrol potential participants into the study, or gain consent. Once all potential participants have been connected with the research team to express their interest, an information day will be conducted by research team members at each site. People who cannot attend the information session will be followed up by the research team.

Potential participants will receive a Participant Information Sheet (see Appendix 12.3) where they can learn more about the research project. Specifically, that participation in the NWG will involve:

- completing an online or pen and paper survey at the commencement and conclusion of the 12-week session,
- completing a brief mood question, pre- and post- each walk,
- participating in a walk once a week for 12 weeks at a location they will be transported to,
- participating in a 2 hour closing focus group at the 12th walk,
- completing one phone interview with a member of the research team, and
- providing 3 saliva samples for cortisol and DHEA testing one week before commencement, at the end of the first walk and conclusion of the last walk but that this will be **optional**.

If people consent to be part of the research, they will be invited to join the first walk. If they do not wish to join the NWG, or if they are not eligible to participate due to the results of the screening assessment (See Appendix 12.7), they will be allocated to Group B and provided a Participant Information Sheet (Appendix 12.4) which will include all details relating to the measures included in the survey to be completed at the beginning and end of a 12 week period, and the optional collection of a saliva sample for cortisol and DHEA testing at the same time as completing the survey.

Informed consent will be obtained from each participant by the research team members at the information event. At least one week following this and one week before the first group walk, all participants will complete the study survey measures, and those participants wishing to participate in the cortisol and DHEA testing will provide a saliva sample. Study co-ordinators will provide assistance and support if required. Study co-ordinators will ensure participants are aware that participation is voluntary, and that participants can withdraw at any time. Participants will also be informed that while the surveys and ethnographic measures will be needed if they wish to participate, they will be told that the salivary testing is optional.

5.5 Intervention (Group A)

A total of four NWG over 12 months will be conducted in the two sites by the trained NWG facilitators. Intervention participants (n=40) will participate in one NWG, receiving 1 hour of time in nature for a continuous period of 12 weeks. Participants will be transported to and from each NWG location by the NWG facilitators. There will be no expectation to socialise with other group members but to remain in the group. Depending on weather variations in each location, the groups may be offered simultaneously or consecutively. Where available an educator such as a National Park ranger can join and refer to points of interest and answer any questions. The project funds will cover all costs of the intervention including backfill for clinicians if required.

5.5.1 *Relaxation and mindfulness activities*

Each NWG will take place in a natural environment, e.g., bush, countryside, National Parks, greenspace in urban areas (e.g., botanical gardens). Each walk will include two activities led by trained facilitator that draw participant's attention to one of the natural features of the site (water, birds, plants) and provide time to reflect on those features. The activities relate to psychological theories that link connection with nature as a pathway to health and wellbeing including Attention Restoration Theory (Ohly et al., 2016), and Stress Reduction Theory (Andrade & Devlin, 2015). Each activity is 2-10 minutes long and is matched with the optimal kind of nature known to facilitate a particular outcome. For example, nature with a high degree of textural diversity is known to be optimal for a stress reduction response. As shown in Table 2, several relaxation and mindfulness routines have been identified for possible inclusion in the NWG, and the study-site co-ordinators will finalise which routines and the locations where they will be used closer to the projects commencement. Each routine will include a script for facilitators to read, or there are audio versions that may be used (for example <https://www.naturefix.life/feel-the-flow>).

Table 2 – Summary of the relaxation and mindfulness activities under consideration for inclusion in the Nature Walking Group

Routine name	Summary	Length (minutes)
1. Tune in to tune out	This abdomen breathing routine takes participants through a simple breathing strategy to take more effective breaths to increase their relaxation and decrease any stress.	2-4
2. Peripheral Power	A vision activity that asks participants to use their wide-angle vision (peripheral vision) to trigger their parasympathetic nervous system that helps them to relax. It involves looking at items that move when looking straight ahead using their full wide-angle vision.	10
3. Fingerprints of Nature	This routine guides participants through viewing the repeated patterns in nature.	5
4. Beauty and Awe	This routine asks participants to look for five (5) beautiful things using all their senses and encouraging them to look in places they don't usually look.	3-10
5. Sounds Good	This routine guides participants to notice sounds in six directions and make a sound map, asking why some places are quiet and others noisy.	3-7
6. Introduce yourself to Country (spoken by [name] - Wiradjuri man)	This routine introduces participants to the traditional First Nations practice of acknowledging Country.	2-3
7. Conscious Breathing	Participants are asked to focus on their natural breathing pattern.	2-3
8. Mindful moments	Participants are asked to engage their sight, touch, sound, smell and taste to mindfully notice the environment.	10
9. Connection on the Move	Participants are asked to engage their peripheral vision, to listen to the environment in six different directions, do a brief body scan, and notice five beautiful things in their environment.	10
10. Give Nature Gratitude	This routine guides participants through selecting a natural item using all their senses to help trigger happy memories and give gratitude to that memory	2-4
11. Reflect and Connect	This routine asks participants to notice larger (trees) and smaller (thumb) elements in their environment.	10

5.5.2 Structure of each Nature Walking Group

Each of the 12 NWG will follow the same format, as follows;

- Transport and housekeeping
 - Participants will either be collected from their homes or will meet at a pre-arranged location at a specified time. Participants will be introduced to one another in the first group.
 - Participants will be transported to the walk locations by the trained facilitators.
 - Supported by social work student (TBC) participants will be asked to individually fill out the before walk mood scale (see Appendix 12.8).
 - Together as a group, facilitators will inform participants of the available facilities and the planned activities for the day.
 - Together as a group, facilitators will ask each participant for feedback on how they were able to implement the relaxation and mindfulness activities between group, as discussed in the previous NWG (this will commence in walk 2).
- Relaxation and mindfulness activities
 - Participants will be invited to participate in one of the pre-selected relaxation or mindfulness routine (see Table 2).
 - An additional routine (see Table 2) will be conducted that will be pre-selected dependent on the site location (e.g. water features, a view).
- Group close
 - Together as a group, participants will be invited to reflect on their experiences on the walk and routines, and asked what mindfulness and relaxation routines they plan to do during the week at home.
 - Participants will complete their after walk mood scale (see Appendix 12.8).
 - Participants are transported home.

5.5.3 Nature Walking Group schedule (TBC)

The exact locations of each walk and routines are to be finalised by each participating service, however, routines and site locations will be selected for appropriateness, and routines will be matched for consistency between sites and group. The NSW National Parks and Wildlife Services grade publicly available walking tracks according to their difficulty (1 to 5, with 5 being the most difficult; please see section 10.5 for further details on this grading). Each selected walk location will be graded between 1-3. Table 3 shows how the walk locations and routines will be matched.

Table 3 - Nature Walking Group schedule - routines and locations (TBC)

Walk/session number	Core routine	Additional routine/s	Site	Walk location (Grade)	Nature characteristics on the walk (e.g. water source, view, textural diversity)
1 [^]	1. Breathe slowly	13. Nature's connections	Orange	Botanic gardens (1)	Textural diversity
			Wollongong	Botanic gardens (1)	Textural diversity
2			Orange		
			Wollongong		
3			Orange		
			Wollongong		
4			Orange		
			Wollongong		
5			Orange		
			Wollongong		
6			Orange		
			Wollongong		
7			Orange		
			Wollongong		
8			Orange		
			Wollongong		
9			Orange		
			Wollongong		
10			Orange		
			Wollongong		
11			Orange		
			Wollongong		
12			Orange		
			Wollongong		

[^]Example routines and location

5.6 Treatment as usual (Groups A and B)

Participants in Group A will also continue to receive one-on-one support from a clinician of the multidisciplinary team at the ICMHS or LikeMind. Similarly, those in the non-walking group will continue their TAU. The teams at each location consist of psychologists, occupational therapists, nurses, social workers and peer workers. The services work with adults (18-65 years old) experiencing varying mental illnesses to support their mental health recovery goals. These goals might revolve around social inclusion, emotional development and support, and vocational support. The sessions are tailored individually, can be held weekly or fortnightly, and can either be brief or long-term support. Clinician support generally involves the use of motivational interviewing, goal setting, problem-solving, case management and some brief cognitive behavioural therapy (CBT). The services assist consumers to develop greater clarity and understanding of their goals and how to achieve them, increase insight into the impacts of mental illness and have greater awareness of resilience factors and community resources.

6 DATA COLLECTION TOOLS AND PROCEDURES

A variety of quantitative and qualitative data will be collected to explore the experiences and impact of NWGs for the participants.

6.1 Organisational Readiness for Implementing Change (ORIC) survey (Group C)

Prior to commencement of the first NWG, employees at each site will be invited to complete an anonymous online survey on the organisational readiness to implement the NWG (see Appendix 12.14). The ORIC is a valid, reliable 12-item questionnaire that assesses the extent to which organisational members are psychologically and behaviourally prepared to implement organisational change.

6.2 Ethnographic observations (Group A)

A research assistant will participate in the walking groups and take field notes following each group. These observations are crucial because they can contribute knowledge of the setting of each group, participants' behavior during each walk, and reflections on the group content and/or process. In this way, the researcher is a participant observer of the walking groups (Creswell, 2013). The fieldnotes will include detailed descriptions and reflections for each entry and may also include theoretical and methodological observations (Emerson, Fretz, & Shaw, 2011). The Ethnographic Observations Guide is attached (see Appendix 12.9).

6.3 Group Closing Reflective Focus Groups (Group A)

After the last group, participants will be invited to take part in a focus group (2 hours). Additionally, field-notes and audio-recording will be taken during the focus group to document participants' reflection on their journey through the program (see Appendix 12.10 for the focus group guide).

6.4 Facilitator focus group (Group C)

After the Nature Walking Groups have finished the Group C will be invited to participate in a 2-hour focus group. The focus groups will be conducted online on Microsoft Teams. The discussion will be audio recorded and recordings will be professionally transcribed into word documents for analysis. Please see Appendix 12.15 for the focus group questions.

6.5 De-identified site-wide client data

To establish the profile of the site's client population and compare it to those participating in the intervention, the evaluation team will utilise a range of de-identified routinely collected health data.

LikeMind and ICMHS will provide de-identified data to the evaluation team.

Data to be extracted;

- Number of clients serviced and their demographics (including diagnosis)
- Referral source
- Intervention activities – type of intervention (e.g. case management, psychiatry), length of time

engaged with service.

- Aggregated outcome measure results

6.6 Pre, post and 3-month follow-up Surveys (Group A and B)

An online or pen and paper survey (See Appendix 12.6) will be completed by participants in groups A and B at baseline, 12 weeks post-baseline (post NWG) and at 3 post-intervention. The following scales will be included:

Table 4 - Pre, post and 3-month follow-up survey scales

Primary Outcome Measure	The Patient Health Questionnaire for Anxiety and Depression (PHQ-AD) (16 items)
Secondary Outcome Measures	Personal Wellbeing Index (7 items)
	Pittsburg Sleep Quality Index (2 items)
	DeJong Gierveld Loneliness Scale (6 items)
	Nature Relatedness Scale – short form (6 items)
	The Warwick Edinburgh Mental Well Being Scale (7 items)
	Major life event, positive or negative (2 items)
	Connor-Davidson Resilience Scale (2 items)

In addition, participants in the NWG will be asked to report their mood pre- and post-walking session, as described in Section 6.8.

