5.2 Training workshop (Group C)

NWG facilitators for each site and the research team will attend training and implementation workshops in February 2024 to provide training to facilitators which ensures adequate practitioner knowledge and skills, and practical guidance on nature routine implementation processes and the participant recruitment and data collection tools. Potential facilitators will be identified by site study co-ordinators (PD and TC) and invited to attend the training workshop.

Table 1 - Data collection methods and corresponding aims

		RE-AIM component				
		Reach	Efficacy	Adoption	Implementation	Maintenance
Aims	Data collection tool (planned data analysis approach)					
1. Implementation of NWG	Organisational readiness survey (Descriptive analysis)			x		
	Ethnographic observations during NWG (Thematic analysis)				x	
	Closing reflective focus group (Thematic analysis)				x	
	Facilitator post focus group (Thematic analysis)			x	x	
	De-identified site wide client data (Descriptive analysis)	x				
	NWG attendance records (Attendance ratio calculations)				x	
2. Impact of NWG	Pre/post and 3 month follow-up survey (Wilcoxon signed ranks)^		x			
	Pre-post salivary cortisol and DHEA testing (Change analysis)		x			
	Before and after mood scale (Change analysis)		x			
1 + 2. Impact and implementation	Phone interviews (Thematic analysis)		x		x	
3. Develop implementation and evaluation guidelines	Member-checking workshop (Thematic analysis)					x
	Site comparisons (Data triangulation)				x	x
	Data guide feedback (Guide draft reviewed)					x

^The Patient Health Questionnaire – Anxiety and Depression Scale is the primary outcome measure.

Key

RE-AIM Component	Reach	Identify characteristics, perceptions, and health service utilisation NWG participants, compared to control.
	Efficacy	Identify changes in nature connection, wellbeing, social isolation, quality of life and confidence/self-esteem for participants and control. Understand what worked for different groups and why.
	Adoption	Explore facilitator and management experiences and the implementation barriers and facilitators. Identify similarities and differences in NWG implementation and impacts between sites.
	Implementation	Monitor the implementation process and the experiences of participants.
	Maintenance	Ensure findings and recommendations reflect the lived experience of participants and inform the NWG implementation and evaluation guide.

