5.3 Sample

The study will have three groups of participants:

- A. Intervention group - people using the mental health services of the partner organisation at the case study sites (n=40) who will participate in the walking groups,
- B. Non-walking group - people using the mental health service of the partner organisation who choose not to participate in the walking groups, but consent to be involved in the research (n=40), and
- C. NWG facilitators - employees of the partner organisations responsible for service delivery at the case study sites (n=10).

Forty participants will be recruited at each site (ICMHS and LikeMind) (n=80) from the mental health consumers receiving services. Approximately 100 consumers receive services at these agencies at any given time.

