7 DATA ANALYSIS

A frequentist statistical approach will be adopted for quantitative data analysis, using SPSS or R software. Specifically, analysis of variance will provide objective evidence of the efficacy of the NWG intervention.

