7.1 Sample size and power calculation

While sample size calculation is crucial for a pilot study, achieving adequate power through formal calculations can be challenging (Billingham et al., 2013). Nonetheless, we have derived the sample size for this study by considering the estimated effect size observed in the literature for various mental health indicators. According to the conceptual framework of the proposed pilot feasibility trial study, the primary outcome measure was the level of distress measured by Patient Health Questionnaire Anxiety and Depression Scale (PHQ-ADS). In a recent randomized controlled trial study in the UK conducted by Picariello et al. (2024), it was found that the mean level of distress among the study participants was 22.76 (SD, 9.46), which decreased by 30% immediately after the cognitive behavioural therapy intervention. We utilized these study findings to inform the parameters for the sample size calculations in our study. We assumed the mean level of distress will be about 22.76 (with SD, 9.46) among the study participants at baseline in both control and interventions group (Picariello et al., 2024). After the program implementation, the mean level of distress will be reduced to 16.08 (SD, 10.41) among the participants in interventions group (assuming about 30% reduction by the intervention; Picariello et al. (2024). To ensure a minimum detectable difference in the mean distress level between the intervention and control groups at follow-up, with a power of 80% and a 5% level of significance, a minimum sample size of 72 participants is required (36 participants in each group). Anticipating 10% loss to follow-up, we plan to include 80 participants in total. Therefore, data will be collected from at least 40 participants in both the control and intervention groups, enabling to assess the program's effectiveness in improving mental health outcomes. Our planned sample size falls within the range of suggested sample sizes for pilot and feasibility studies as per the guidelines, which recommend 30-59 participants (Billingham et al., 2013; Viechtbauer et al., 2015).

The outcomes will be analysed using a Wilcoxon signed ranks test to calculate change between scores because measures contain ordinal data and a test that does not assume a normal distribution is required. A W-statistic is appropriate for a small number of linked observations.

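### Major life events are classed as a secondary outcome and sent to an efficacy test, although the item has no direction of benefit; it belongs with the context and covariate measures

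*Protocol*

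**What the plan says.** Table 4 (Protocol, Section 6.6) gives each survey measure one of two roles, primary or secondary outcome. PHQ-ADS is primary. Seven measures are secondary, and one of them is "Major life event, positive or negative (2 items", placed between a wellbeing scale and a resilience scale. The survey is "completed by participants in groups A and B at baseline, 12 weeks post-baseline (post NWG" and again three months after the intervention.

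Table 1 (Section 5.2) has the line "Pre/post and 3 month follow-up survey (Wilcoxon signed ranks" and marks it under Efficacy. Its key defines that component as: "Identify changes in nature connection, wellbeing, social isolation, quality of life and confidence/self-esteem for participants and control". Section 7.1 states: "The outcomes will be analysed using a Wilcoxon signed ranks test to calculate change between scores". Section 7 says, more generally, that "analysis of variance will provide objective evidence of the efficacy of the NWG intervention".

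The groups are not randomised. Section 5.3 describes Group B as "people using the mental health service of the partner organisation who choose not to participate in the walking groups". Sections 5.3.2 and 5.4 add people who do not pass the health assessment or whose physician judges them unable to take part.

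**The concern.** An efficacy outcome needs a direction in which change is good. An item that covers both welcome and unwelcome events has none as labelled, and the protocol nowhere says that the programme is meant to change how often such events occur. A significant signed ranks result on it would have no efficacy meaning, yet it would stand in the results beside wellbeing, sleep and loneliness.

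The label also hides a better use. Recent major events may be related both to willingness to join a 12-week programme and to distress. Where people choose their group, a baseline answer already collected from everyone is a natural adjustment variable. Classing it as an outcome points the analyst away from that.

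**Working it through.** The point turns on how the sections fit together, so they are set side by side. The one related figure, the sample size, is checked last.

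1. **Role.** Table 4 has 1 primary and 7 secondary measures. Life events are 1 of the 7. The table has no context or covariate category.

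2. **Test.** Table 1 sends the survey as a whole to a signed ranks test under Efficacy, and Section 7.1 applies the test to the outcomes without exception. Together they include the life-event items.

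3. **Efficacy definition.** The key to Table 1 names nature connection, wellbeing, social isolation, quality of life and confidence or self-esteem. The occurrence of life events is not there. The key goes on to seek an understanding of what worked for whom and why, which is where a context measure fits.

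4. **What the test would return.** A signed ranks test needs an ordered score. Suppose, for illustration, that any event scores 1 and none scores 0. Someone with no event at baseline and a serious loss by 12 weeks has a change of 1 − 0 = +1. So does someone with a welcome new job. The test treats them alike. If the two items instead separate positive from negative events, each can be ordered, but the protocol still states no hypothesis that walking changes its frequency.

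5. **Timing.** The baseline survey is completed before the first walk (Section 5.4), so events reported then cannot result from the programme. Events reported at 12 weeks and 3 months may have occurred after group entry. They may be prognostic, but they may also lie on the path from programme to distress, so routine adjustment for them could remove part of an effect.

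6. **Model.** A signed ranks test is a paired test within one group. It takes no covariate and makes no between-group contrast. The analysis of variance in Section 7 can be extended to a linear model with covariates.

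7. **Sample size (Section 7.1).** Difference: 22.76 − 16.08 = 6.68. Common SD: √[(9.46² + 10.41²)/2] = 9.946. Standardised difference: 6.68/9.946 = 0.672. With 80% power and a two-sided 5% level (sidedness is not stated), the normal approximation gives 35 per group and the t-test version 35.8, so 36 per group and 72 in total. Allowing 10% loss, 72/0.90 = 80. The plan's figures reproduce, and no life-event quantity enters them.

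**The case against.** The strongest reply is that this is only a label. No sentence gives life events a hypothesis or calls a change in them a benefit, the item wording is in an appendix that was not available, and the choice of covariates is normally left to a statistical analysis plan. Much of that stands. The point therefore does not rest on a missing covariate model. It rests on what the protocol does state: an outcome label combined with an analysis rule that has no exception. Absence from the efficacy key is supporting evidence only, since sleep is not named there either; the lack of direction carries the argument.

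A reader might infer four stronger things that the protocol does not support:

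- **That walking cannot cause life events.** Nothing excludes it. The Background says group programmes create social connections, and the events that count are not defined.
- **That the protocol tests life events as a benefit.** This comes only from reading Table 1, Table 4 and Section 7.1 together; it is not stated.
- **That this is one of few available confounders.** Every Table 4 scale is collected at baseline in both groups, and baseline PHQ-ADS is the obvious first adjustment.
- **That the bias can be sized.** If an event shifted PHQ-ADS by 3 to 7 points and its frequency differed by 10 to 30 percentage points between groups, the bias would run from 3 × 0.10 = 0.3 to 7 × 0.30 = 2.1 points, or 4% to 31% of 6.68. Both inputs are assumptions with no basis in the protocol. The product also describes an unadjusted follow-up comparison; with change scores, an event that had already raised baseline distress is at least partly differenced out.

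**Conclusion.** The misclassification stands. Read together, Tables 1 and 4 and Section 7.1 put an item with no direction of benefit through an efficacy change test, and the result could not be interpreted as efficacy. The item is better treated as a prognostic or context measure in a comparison of self-selected groups.

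The consequence is small: one of seven secondary measures, with no effect on the definition of the primary outcome or on the 36 per group, 72 and 80. Whether life events actually differ between the groups, and by how much that would distort the PHQ-ADS comparison, is unknown. The case for using the baseline answer as a covariate assumes only that recent events may be related to both group choice and distress.

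**What to change.** In Table 4, move the life-event items out of the secondary outcomes into a row for context and covariate measures. In Table 1 and Section 7.1, exclude them from the signed ranks efficacy tests.

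In Section 7, state that the between-group PHQ-ADS comparison uses a linear (ANCOVA-type) model with group, baseline PHQ-ADS and the baseline life-event answer. This fits the analysis-of-variance approach already named there; the signed ranks test cannot do it. Report events at 12 weeks and 3 months by group descriptively, or in a sensitivity analysis labelled as such, because they may be mediators.

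No new data are needed. The life-event term costs one or two degrees of freedom, depending on how the two items are coded. The edit is more than a table change, because the between-group model must be written down.
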